4.1. Primary Objective

The primary objective of the study is to demonstrate that tirzepatide 10 mg and/or 15 mg once-weekly (QW) are superior to placebo for percent change in body weight from randomization **and** percentage of participants who achieve $\geq 5\%$ body weight reduction at 72 weeks.

4.2. Key Secondary Objectives

Together with the primary objective, the following secondary objectives are subjected to strong control of the type 1 error rate (see Section 6.13.3).

- To demonstrate that pooled tirzepatide 10 mg and 15 mg QW is superior to placebo for change in body weight (kg) from randomization at 20 weeks.
- To demonstrate that tirzepatide 5 mg QW is superior to placebo for percent change in body weight from randomization **and** percentage of participants who achieve $\geq 5\%$ body weight reduction at 72 weeks.
- To demonstrate that tirzepatide 10 mg and/or 15 mg QW are superior to placebo for percentage of participants who achieve $\geq 10\%$ body weight reduction from randomization at 72 weeks.
- To demonstrate that tirzepatide 10 mg and/or 15 mg QW are superior to placebo for percentage of participants who achieve $\geq 15\%$ body weight reduction from randomization at 72 weeks.
- To demonstrate that tirzepatide 10 mg and/or 15 mg QW are superior to placebo for the percentage of participants who achieve $\geq 20\%$ body weight reduction from randomization at 72 weeks.
- To demonstrate that tirzepatide 10 mg and/or 15 mg QW are superior to placebo for change from randomization in waist circumference (cm) at 72 weeks.
- To demonstrate that pooled tirzepatide 10 mg and 15 mg QW is superior to placebo for change in Short Form -36 version 2 Health Survey (SF-36v2) acute form Physical Functioning domain score from randomization at 72 weeks.
- To demonstrate that tirzepatide QW (all doses combined) is superior to placebo for change in triglycerides (mg/dL) from randomization at 72 weeks.
- To demonstrate that tirzepatide QW (all doses combined) is superior to placebo for change in non-high-density lipoprotein cholesterol (non-HDL-cholesterol) (mg/dL) from randomization at 72 weeks.
- To demonstrate that tirzepatide QW (all doses combined) is superior to placebo for change in - high-density lipoprotein cholesterol (HDL-cholesterol) (mg/dL) from randomization at 72 weeks.
- To demonstrate that tirzepatide QW (all doses combined) is superior to placebo for change in systolic blood pressure (SBP) (mmHg) from randomization at 72 weeks.

- To demonstrate that tirzepatide QW (all doses combined) is superior to placebo for change in fasting insulin (pmol/L) from randomization at 72 weeks.
- To demonstrate that tirzepatide 10 mg and/or 15 mg QW are superior to placebo for percent change in body weight from randomization at 176 weeks (for participants with prediabetes at randomization).
- To demonstrate that tirzepatide QW (all doses combined) is superior to placebo for delaying the onset of type 2 diabetes mellitus (T2DM) during 176 weeks (for participants with prediabetes at randomization).
- To demonstrate that tirzepatide QW (all doses combined) is superior to placebo for delaying the onset of T2DM during 193 weeks (for participants with prediabetes at randomization).

4.3. Other Secondary Objectives

The following secondary objectives are not subjected to strong control of the type 1 error rate:

[figure not shown]
- to demonstrate that tirzepatide 5 mg QW is superior to placebo at 72 weeks for
 - percentage of participants who achieve $\geq 10\%$ body weight reduction from randomization
 - percentage of participants who achieve $\geq 15\%$ body weight reduction from randomization
 - mean change in waist circumference (cm) from randomization, and
 - mean change in SF-36v2 acute form Physical Functioning domain score from randomization.
- to demonstrate that tirzepatide 5 mg, 10 mg, and/or 15 mg QW are superior to placebo at 72 weeks for
 - mean change in body weight (kg) from randomization
 - mean change in body mass index (BMI) (kg/m^2) from randomization
 - mean change in hemoglobin A1c (HbA1c) (% , mmol/mol) from randomization
 - mean change in fasting glucose (mg/dL) from randomization
 - mean change in Impact of Weight on Quality of Life-Lite-Clinical Trials Version (IWQOL-Lite-CT) Physical Function composite score from randomization
- to demonstrate that tirzepatide QW (all doses combined) is superior to placebo at 72 weeks for
 - mean change in diastolic blood pressure (DBP) (mmHg) from randomization
 - mean change from randomization in the following lipid parameters:
 - low-density lipoprotein cholesterol (LDL-cholesterol)(mg/dL)
 - total cholesterol (mg/dL)

- very low-density lipoprotein cholesterol (VLDL-cholesterol)(mg/dL)
- free fatty acids (mg/dL)
- to demonstrate that tirzepatide 5 mg QW is superior to placebo for percent change in body weight (kg) from randomization at 176 weeks (for participants with prediabetes at randomization)
- to demonstrate that tirzepatide 5 mg, 10 mg, and/or 15 mg QW are superior to placebo for percentage of study participants who achieve $\geq 5\%$ body weight reduction from randomization at 176 weeks (for participants with prediabetes at randomization), and
- to demonstrate that tirzepatide QW (all doses combined) is superior to placebo (for participants with prediabetes at randomization) at 176 weeks for:
 - change in SF-36v2 acute form Physical Functioning domain score from randomization and
 - change in IWQOL-Lite-CT Physical Function composite score from randomization.

5. Study Design

5.1. Summary of Study Design

Study I8F-MC-GPHK (GPHK; SURMOUNT-1) is a Phase 3, multicenter, randomized, placebo-controlled, double-blinded study of the safety and efficacy of 5 mg, 10 mg, and 15 mg tirzepatide QW, compared with placebo, when used in conjunction with a reduced-calorie diet and increased physical activity for weight management, in participants who do not have T2DM, and have obesity (BMI ≥ 30 kg/m²) or are overweight (BMI ≥ 27 kg/m²) with at least 1 weight-related comorbid condition (for example, hypertension, dyslipidemia, or cardiovascular disease). All participants will be randomized to at least 72 weeks of treatment to study the effects on body weight reduction. Participants who have prediabetes will be studied for a total of 176 weeks of treatment to provide sufficient follow-up time to detect potential differences in progression to T2DM.

Abbreviations: QW = once weekly; T = telephone visit; T2DM = type 2 diabetes mellitus.

Note: All participants (regardless of prediabetes status [Y/N] at screening) will be randomized to at least 72 weeks of treatment to study the effects on body weight reduction. Participants who have prediabetes will continue for a total of 176 weeks of treatment to provide sufficient follow-up time to detect potential differences in progression to T2DM. The safety follow-up visit will occur after 4 weeks in participants discontinuing (or completing) the study within the first 72 weeks. Those discontinuing (or completing) the study after 72 weeks will undergo safety follow-up after 17 weeks.

Figure GPHK.5.1. Illustration of study design for Clinical Protocol I8F-MC-GPHK.

The details about the overview of study periods and study visits can be found in Study GPHK protocol Section 4. The detail of the unique visits not displayed in Figure GPHK.5.1. is provided below.

Visit 99

Visit 99 is only applicable to participants who discontinue the study treatment prematurely prior to Visit 21 (Week 72). Participants will be asked to return for Visit 99 at 72 weeks \pm 7 days after randomization. This visit is critical to ensure complete data collection for the primary weight-loss endpoint.

Participants should attend this visit in the fasting state. Procedures to be completed include

- measurement of weight and waist circumference
- concomitant medications
- assessment of adverse events (AEs), and

- completion of the mental health questionnaires (after the AE assessment).

Visit 199

Visit 199 is only applicable to participants who discontinue the study treatment prematurely after Visit 21 (Week 72) and prior to Visit 116 (Week 176). Participants will be asked to return for Visit 199 at 176 weeks \pm 7 days after randomization. This visit is critical to ensure complete data collection for the weight-loss and progression-to-diabetes endpoints.

Participants should attend this visit in the fasting state. Procedures to be completed include

- measurement of weight and waist circumference
- concomitant medications
- assessment of AEs
- completion of the mental health questionnaires (after the AE assessment), and
- 2-hour oral glucose tolerance test (OGTT).

Early Discontinuation of Treatment Visit

Participants unable or unwilling to continue the study treatment for any reason will perform early discontinuation of treatment (ED) visit at the visit when the participant informs the site about the study treatment discontinuation.

6. A Priori Statistical Methods

6.1. Populations for Analyses

For purposes of analyses, [Table GPHK.6.1](#) defines the analysis sets.

Table GPHK.6.1. Description of Analysis Datasets

Analysis Set	Description
Entered Participants	All participants who sign informed consent
Randomized Participants	All participants who are randomly assigned a study treatment
Modified Intent-to-Treat (mITT)	All randomly assigned participants who are exposed to at least 1 dose of study drug. Participants will be included in the treatment group they were randomized to.
Efficacy Analysis Set (EAS)	Data obtained during treatment period from mITT, excluding data after discontinuation of study drug (last dose date + 7 days).
Full Analysis Set (FAS)	Data obtained during treatment period from mITT, regardless of adherence to study drug.
Safety Analysis Set (SS)	Data obtained during the treatment period plus safety follow-up period from mITT, regardless of adherence to study drug.

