6.5. Concomitant Therapy

Participants will be permitted to use concomitant medications that they require during the study, except certain medications (for example; other medications for weight management) that may interfere with the assessment of efficacy and safety characteristics of the study treatments.

Participants who develop diabetes during the study may initiate medication for glucose control, with the exception of DPP-4 inhibitors or GLP-1R agonists (Section 4.1.2.3). Initiation of metformin for the treatment of diabetes is permitted, but metformin should not be initiated during the study for the treatment of other metabolic conditions (for example, polycystic ovary syndrome, diabetes prevention).

Investigative-site staff will inform participants that they must consult with the investigator or a designated site staff member upon being prescribed any new medications during the study. This may not be possible when initiated for treatment of medical emergencies, in which case, the participant will inform the investigator or a designated site staff member as soon as possible.

Nonstudy medications taken by participants who are screened but not randomized will not be reported to Lilly unless an SAE or AE occurs that the investigator believes may have been caused by a study procedure.

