7.1. Discontinuation of Study Intervention

Possible reasons leading to permanent discontinuation of IP:

- **participant decision**
 - the participant requests to discontinue IP.
- **clinical considerations**
 - initiation of open-label GLP-1R agonist or DPP-4 inhibitor, if participants will not or cannot discontinue them
 - intolerable GI symptoms despite management as described in Section 6.6.2
 - BMI ≤ 18.5 kg/m² is reached at any time during the treatment period
 - Note:* The investigator should contact the Sponsor CRP to discuss whether it is medically appropriate for the participant to continue study treatment.
 - diagnosis of T1DM
 - diagnosis of MTC after randomization
 - significant elevation of calcitonin (Section 10.3.1.4)
 - diagnosis of acute or chronic pancreatitis
 - diagnosis of an active or untreated malignancy (other than basal or squamous cell skin cancer, in situ carcinomas of the cervix, or in situ prostate cancer) after randomization
 - development of any significant study drug-related hypersensitivity reaction
 - onset of pregnancy in a female participant
 - occurrence of any other treatment-emergent AE (TEAE), SAE, or clinically significant finding for which the investigator believes that permanent study drug discontinuation is the appropriate measure to be taken
 - inadvertent enrollment if continued treatment with study drug would not be medically appropriate (Section 7.2.3)
 - PHQ-9 score ≥ 15

- Participants should be referred to a Mental Health Professional (MHP) to assist in deciding whether the subject should be discontinued from study drug. If a participant's psychiatric disorder can be adequately treated with psycho- and/or pharmacotherapy, then the subject, at the discretion of the Investigator (in agreement with the MHP), may be continued in the trial on randomized therapy.
- in addition, study drug may be discontinued if participants:
 - answered "yes" to either Question 4 (Active Suicidal Ideation with Some Intent to Act, Without Specific Plan) on the "Suicidal Ideation" portion of the C-SSRS
 - or**
 - answered "yes" to Question 5 (Active Suicidal Ideation with Specific Plan and Intent) on the "Suicidal Ideation" portion of the C-SSRS
 - or**
 - answered "yes" to any of the suicide-related behaviors (Actual attempt, Interrupted attempt, Aborted attempt, Preparatory act or behavior) on the "Suicidal Behavior" portion of the C-SSRS.

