9.3. Populations for Analyses

For purposes of analysis, the following analysis sets are defined:

Analysis Set	Description
Entered Participants	all participants who sign informed consent
Randomized Participants	all participants who are randomly assigned a study treatment
Modified Intent-to-Treat (mITT)	all randomly assigned participants who are exposed to at least 1 dose of study drug; participants will be included in the treatment group they were randomized to
Efficacy Analysis Set (EAS)	data obtained during treatment period from mITT, excluding data after discontinuation of study drug (last dose date + 7 days)
Full analysis set (FAS)	data obtained during treatment period from mITT, regardless of adherence to study drug.
Safety Analysis Set (SS)	data obtained during the treatment period plus safety follow-up period from mITT, regardless of adherence to study drug

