Table GPHK.6.2. Baseline and Postbaseline Definitions for Safety Groups

Analysis Set	Analysis Type	Baseline	Postbaseline
SS	1.1) Treatment-Emergent Adverse Events	The baseline period is defined as the start of screening and ends prior to the first dose of study treatment (typically at Week 0).	Starts after the first dose of study treatment and ends at the end of the study period (including off-drug follow up visit).
SS	1.2) Treatment-Emergent Abnormal Labs ^a , Vital Signs, and ECGs.	Baseline will include all scheduled and unscheduled measurements during the baseline period (Visit 1 to Visit 3)	Postbaseline will be defined as measurements after Visit 3 . All scheduled and unscheduled measurements will be included.
SS	1.3) Change from Last Baseline to Week xx and to Last Postbaseline for Labs ^a , Vital Signs, and ECGs.	The last scheduled and unscheduled non-missing assessment recorded during the baseline period defined above (1.2).	Postbaseline will be defined as above (1.2). Only scheduled visits will be included. The early discontinuation (ED) visits are considered scheduled visits.

Abbreviations: ECGs = electrocardiogram; SS = Safety Analysis Set.

^a Immunogenicity related analysis is specified in Section [6.14.3.7](#).

There will be 2 estimands of interest in evaluating primary and key secondary efficacy objectives:

- For objectives controlled for Type 1 error at 72 weeks:
 - the “efficacy” estimand, defined as the average treatment effect of tirzepatide relative to placebo at 72 weeks, as an adjunct to a reduced-calorie diet and increased physical activity, in the randomized participants had they remained on their randomized treatment for the entire planned 72 weeks treatment duration.
 - the “hybrid” estimand, is the average treatment effect of tirzepatide relative to placebo at 72 weeks, as an adjunct to a reduced-calorie diet and increased physical activity, for the randomized participants regardless of the adherence to treatment

- For objectives controlled for Type 1 error assessed after 72 weeks:
 - the “efficacy” estimand, defined as the treatment effect of tirzepatide relative to placebo at 176/193 weeks, as an adjunct to a reduced-calorie diet and increased physical activity, in the randomized participants with prediabetes at randomization had they remained on their randomized treatment for the entire planned 176 weeks treatment duration.

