6.10. Concomitant Therapy

Concomitant medication will be summarized by PTs by treatment group by decreasing frequency for SS group. The following 2 postbaseline periods will be considered, respectively:

- up to 72 weeks plus safety follow-up (Visit 801) for all randomized participants, and
- up to 176 weeks plus safety follow-up (Visit 801 or Visit 802) for participants with prediabetes at randomization.

Additionally, medications of interest (as defined below) will be summarized by treatment for SS.

Concomitant medications of interest include the following:

- baseline antihypertensive therapy
- baseline lipid lowering therapy
- changes to baseline medication in post-randomization (in term of type/class and dose):
 - antihypertensive therapy, and
 - lipid lowering therapy.
- utilization after randomization of:
 - antihyperglycemic medication for the treatment of diabetes for participants who develop T2DM during the study (antihyperglycemic medication for the treatment of prediabetes is not allowed pre protocol)
 - antidiarrheal medication. and
 - antiemetic medication.

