6.13.1.1. Analysis Related to the Efficacy Estimand

The analysis related to efficacy estimand will be conducted utilizing data in the EAS.

For the mean percent body weight change from randomization, a MMRM will be conducted. Restricted maximum likelihood (REML) will be used to obtain model parameter estimates and the Kenward-Roger option will be used to estimate the denominator degrees of freedom. The response variable of MMRM will be the percent change in body weight from baseline values obtained at each scheduled post baseline visit.

For the percentage of participants achieving at least 5% body weight reduction from randomization over time, a logistic regression model will be used with the response variable of the percentage of participants achieving at least 5% body weight reduction at each scheduled postbaseline visit.

For MMRM the independent variables of analysis model is treatment group, visit, treatment-by-visit interaction, stratification factors (prediabetes status at randomization, sex and country/pooled country) as fixed effects, and baseline body weight as a covariate. An unstructured covariance structure will model relationship of within-patient errors. If this model fails to converge, the following variance covariance structures will be tested in order until convergence is achieved:

- heterogeneous Toeplitz
- heterogeneous first order autoregressive
- heterogeneous compound symmetry
- Toeplitz
- first order autoregressive, and
- compound symmetry.

The first covariance structure that converges will be used.

With the aid of the MMRM analysis, 2-sided 95% CIs for mean percent change in body weight from randomization to the 72-week visit for tirzepatide 10 mg and 15 mg compared to placebo will be derived and summarized. The resulting least squares mean (LSM) estimates of mean percent change in body weight from baseline will be plotted by visit and by study treatment.

A logistic regression model with terms of treatment group, country/pooled country, sex, and prediabetes status at randomization as fixed effects, and baseline body weight as a covariate, will be conducted for percentage of participants achieving at least 5% body weight reduction from randomization at the 72 week visit. Missing body weight measurement at 72 week will be imputed by the predicted value from MMRM model aforementioned, then the continuous measurements will be dichotomized into status of achieving at least 5% body weight reduction

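### The Efficacy Analysis Set has no rule for weights taken after other weight-loss treatment starts while study drug continues, so they count by default as the effect of randomised treatment

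*SAP*

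**What the plan says.** - **Data cut.** Table GPHK.6.1 in SAP 6.1 defines the EAS as "Data obtained during treatment period from mITT, excluding data after discontinuation of study drug (last dose date + 7 days"). Protocol 9.3 has the same definition: "data obtained during treatment period from mITT, excluding data after discontinuation of study drug (last dose date + 7 days"). Neither gives a second reason for removing data.
- **Use of the set.** SAP 6.13.1.1: "The analysis related to efficacy estimand will be conducted utilizing data in the EAS". It adds no further exclusion. The mixed model for repeated measures (MMRM) is fitted to these data. The responder analysis fills missing Week 72 weights from that model and then dichotomises them.
- **Estimand.** SAP 6.2 asks for the effect "as an adjunct to a reduced-calorie diet and increased physical activity, in the randomized participants had they remained on their randomized treatment". The only condition on conduct after randomisation is staying on randomised treatment.
- **Other weight-loss treatment.** Protocol 6.5 permits concomitant drugs "except certain medications (for example; other medications for weight management) that may interfere with the assessment of efficacy". Protocol 4.1.2.3 prohibits open-label GLP-1 receptor agonists. Protocol 7.1 lists, among possible reasons to stop study drug permanently, "initiation of open-label GLP-1R agonist or DPP-4 inhibitor, if participants will not or cannot discontinue them". It has no specific entry for other weight-loss drugs or for obesity procedures. Section 5.2 covers prior weight-loss drugs, and prior or planned procedures, as entry exclusions.
- **Intercurrent events.** SAP 6.13.1.3 addresses them for the hybrid estimand only, and only through the missing values that result.
- **Reporting.** SAP 6.10 summarises all concomitant medication by arm and then lists medications of interest. Weight-management drugs are not on that list.

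**The concern.** The plan names a class of drugs that can distort the efficacy comparison, bars them, and then does not say what happens to weights recorded when someone takes them anyway. Because the EAS cut depends on study drug alone, those weights are kept and read as the effect of the assigned arm. A participant on placebo who adds a weight-loss drug and goes on injecting is analysed as a participant on placebo and lifestyle advice.

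Participants who are losing little weight have the most reason to add treatment, so more use on placebo is plausible, and that would dilute the estimated difference. More use on tirzepatide would inflate it. Either way the estimate would carry a component that is not the randomised treatment. It would do so under the estimand meant for publications and non-FDA agencies, for both co-primary endpoints, the higher responder thresholds and percent weight change at 176 weeks.

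**Working it through.** **1. Does any other text remove these weights?** Taking each kind of added treatment while study drug continues:

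| Added treatment | Event that could stop study drug, and so end EAS data | What stays in the EAS |
|---|---|---|
| Open-label GLP-1 receptor agonist, persistent | Listed in protocol 7.1 as a possible reason to stop | Weights up to last dose + 7 days |
| Open-label GLP-1 receptor agonist, transient | Not reached, since the participant stops the agonist | All weights |
| Other weight-management drug | No specific entry | All weights, unless study drug happens to stop |
| Obesity procedure | No specific entry | All weights, unless study drug happens to stop |

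The gap is therefore complete for the last three rows and partial for the first.

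**2. The plan's own power figure.** Inputs from protocol 9.2: difference 11 points, SD 10, 600 per arm, 25% dropout, two-sided alpha 0.025 per dose. Then n = 600 × 0.75 = 450 per arm.

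- SE = 10 × √(2/450) = 0.667 points.
- Power = Φ(11/0.667 − 2.24) = Φ(14.3), above 99.9%. The stated figure of more than 90% is met.
- Smallest difference with 90% power: (2.24 + 1.28) × 0.667 = 2.35 points.
- 95% CI half-width: 1.96 × 0.667 = 1.31 points.

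**3. Size of the shift in the mean.** Let f be the share of an arm whose Week 72 weight is kept while affected by added treatment, and d the extra loss in percentage points. Then

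EAS difference = 11 − (f_placebo − f_tirzepatide) × d.

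The documents give neither f nor d. The values below are assumptions.

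| f placebo | f tirzepatide | d = 5 | d = 10 |
|---|---|---|---|
| 2% | 0% | 10.90 | 10.80 |
| 5% | 0% | 10.75 | 10.50 |
| 10% | 0% | 10.50 | 10.00 |
| 10% | 2% | 10.60 | 10.20 |
| 0% | 2% | 11.10 | 11.20 |

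With use on placebo only, the shrinkage runs from 0.02 × 5 = 0.1 to 0.10 × 10 = 1.0 points. The largest value is 1.0/11 = 9% of the planned difference and lies inside the CI half-width of 1.31. The last row shows the sign reversing. Every difference in the table is far above 2.35, and power stays above 99.9%.

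**4. Responders at ≥5%, as an upper bound.** Protocol 9.2 assumes 25% on placebo and 90% on tirzepatide, an odds ratio of (0.90/0.10)/(0.25/0.75) = 27.0. If every placebo user became a responder, the placebo rate would be 0.25 + f × 0.75:

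- f = 2%: 26.5%, odds ratio 25.0
- f = 5%: 28.75%, odds ratio 22.3
- f = 10%: 32.5%, odds ratio 18.7

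These are ceilings, since not every user would cross the threshold.

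**The case against.** The strongest reply is that the plan is consistent with itself. The estimand is conditioned on participants "in the randomized participants had they remained on their randomized treatment for the entire planned 72 weeks treatment duration", and the EAS removes data when they do not. Keeping weights after added therapy is a treatment-policy choice for that event, and nothing in the text requires a hypothetical strategy instead. This stands in part: there is no contradiction. But the choice is never stated, and it sits awkwardly with an otherwise hypothetical estimand and with protocol 6.5's own warning about interference.

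Some stronger readings are tempting, and the documents do not support them.

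- **That the estimand excludes other weight-loss therapy in terms.** A reader might infer this from the adjunct wording, but the definition does not say that diet and activity are the only accompaniments.
- **That such use would go unreported.** SAP 6.10 summarises all concomitant medication by arm, and SAP 6.12 summarises important deviations, whose definitions are in a separate plan. What is missing is a targeted summary.
- **That the bias must run against tirzepatide.** More use on placebo is plausible but not documented.
- **That the higher responder thresholds are badly distorted.** Large proportional effects on their odds ratios need a normal model that the plan does not anchor. With SD 10 and 25% placebo responders the placebo mean is −5 + 6.74 = +1.74. Subtracting 11 gives −9.26, which implies about 66% ≥5% responders on tirzepatide against the 90% assumed. (The plan says at least 11 points, so this is a loose fit rather than an error.)
- **That off-protocol glucose-lowering drugs call for censoring in the type 2 diabetes analysis.** SAP 6.10 tracks "antihyperglycemic medication for the treatment of diabetes for participants who develop T2DM during the study", and a reader might infer that other use hides events. But protocol 4.1.2.3 makes starting any drug to treat diabetes an incident-diabetes event, and protocol 6.5 bars metformin for prevention. Censoring the remaining use could itself be informative, since those participants may be the ones whose glucose is rising.

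**Conclusion.** The concern holds as an unaddressed intercurrent event under the efficacy estimand. The EAS keeps weights affected by other weight-loss treatment whenever study drug continues. Persistent GLP-1 receptor agonist use is partly covered through protocol 7.1. Transient use, other weight-management drugs and obesity procedures are not.

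The size is likely modest. With 2-10% use on placebo, none on tirzepatide and 5-10 points of extra loss, the 11-point difference shrinks by 0.1-1.0 points. All three inputs are assumptions, and the sign follows whichever arm uses more. What is affected is the estimate and its interpretation. The conclusion of superiority and the power are not at risk, and the hybrid analysis for the FDA does not use the EAS.

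**What to change.** 1. In SAP Table GPHK.6.1 and protocol 9.3, end EAS weight data at the earlier of last dose plus 7 days and the recorded start of a prohibited weight-management drug, an open-label GLP-1 receptor agonist, or an obesity procedure (where recorded). The existing MMRM then treats later weights as missing, and the responder analysis follows from it.
2. Add weight-management drugs and obesity procedures to the SAP 6.10 summary of medications of interest, by arm.
3. Report the current EAS definition as a sensitivity analysis, so that the effect of the rule can be seen.
4. Leave the hybrid analysis on the Full Analysis Set and the type 2 diabetes analysis unchanged. The change concerns which data are analysed; it alters no rule for treating participants or stopping study drug.

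**Cost.** Text changes, best made before unblinding. Concomitant medication is already collected at every scheduled visit. Procedures are less certain: the schedules of activities have no post-baseline item for them, and protocol 8.3 says planned surgery is not reported as an adverse event unless the underlying condition worsened. That part can rest only on what happens to be recorded. The statistical price is a small loss of EAS data and reliance on missing at random after added treatment starts. The MMRM does use each participant's earlier weights, but the data cannot test the assumption.
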